## 3.5.4 Global Rating Scale (perception of changes in oral condition)

At the interim and final visits, we will assess patients' perceptions of the changes in the oral condition on a 5 item scale (worsened greatly, worsened somewhat, stayed the same, improved somewhat, improved greatly). The data will be correlated with the results from the numerical scoring systems to assess internal validity (**Appendix D**).

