## 6.2 ORAL GVHD SEVERITY SCALES

The primary endpoint will be evaluated using expanded oral GVHD severity scale (**Appendix** A). There is no standard definition of response in this field. The definitions we will use in this pilot study to grade the level of response to study intervention will be as follows:

- **Progression (PD):** defined as increase of 25% of initial score (rounded to the closest number) on the OMRS scale (Appendix A).
- **Partial Response (PR):** defined as decrease of 25% of initial score (rounded to the closest number) on the OMRS scale (**Appendix A**).
- Complete Response (CR): defined as score of 0 on the erythema and ulceration components of the OMRS scale (Appendix A).
- Stable Disease (SD): does not meet criteria for progression or response.

For the purpose of OMRS instrument evaluation validation, we will also use a simplified scale developed for assessment of cGVHD response in the oral cavity (Appendix B). Scoring will be performed by investigators trained in assessment of oral cavity lesions. As part of the evaluation

of the scales, the results will be correlated with scores from symptom-oriented instruments and global scale.

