## **10.2** STATISTICAL CONSIDERATIONS

The primary objective of this randomized pilot study is to determine if the use of clobetasol may result in improvement or stabilization in outcomes in patients with oral chronic GVHD. An important secondary objective is to preliminarily validate and explore the utility of the response measurement instruments.

Patients with oral cGVHD meeting the eligibility criteria will be separately randomized to either 1 month of clobetasol 0.05% oral rinse or placebo; there will not be separate accrual goals for each age group or type of underlying disease. The patients will be followed every 2 weeks for 1 month for their primary endpoint, and once 1 month after completion of study agents.

The primary endpoint will be the change in OMRS score (**Appendix A**) after 1 month of clobetasol 0.05% oral rinse compared to baseline. We will consider a 25% or larger decrease in the score to be clinically significant and a 'response' for the purpose of this study. As this is a pilot study, the association between this level of change and other scales will also be assessed to determine if this is a meaningful measure to use in future trials or if modification is warranted. Thus, this study will be a pilot for the determination of a meaningful response as well for determining if the agent tested may be beneficial.

After the first 2 weeks of clobetasol treatment, patients can be removed from study if oral disease progression is documented. Patients who are taken off study for oral disease progression will be counted as non-responders at the time of the final analysis. Patients taken off study for non-compliance, specifically  $\geq$ 75% non-use of the oral rinse, will not be included in the data analysis

The patients enrolled on this study may be a very heterogeneous group with respect to prior treatments, extent of disease, etc. Patients taken off study for reasons unrelated to the primary outcome will be classified as non-responders and analyzed accordingly. The results will be interpreted in the context of a pilot study with potential limitations noted.

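### Testing the 25% OMRS response cut alone against other scales cannot show whether 25% or some other cut is the meaningful one

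*Combined protocol and SAP*

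**What the plan says.** Section 10.2 sets the response definition: "We will consider a 25% or larger decrease in the score to be clinically significant". It then explains how that value will be judged: "the association between this level of change and other scales will also be assessed to determine if this is a meaningful measure", and the sentence goes on "to use in future trials or if modification is warranted". The paragraph ends by saying that "this study will be a pilot for the determination of a meaningful response" as well as of the agent.

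Section 6.2 gives the reason for asking: "There is no standard definition of response in this field". It adds that, in evaluating the scales, "the results will be correlated with scores from symptom-oriented instruments and global scale". Section 3.5.4 says of the global rating: "The data will be correlated with the results from the numerical scoring systems to assess internal validity".

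No section names an alternative cut, an anchor that defines meaningful improvement, a test for the association, or a result that would lead to modification.

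**The concern.** The question in section 10.2 is comparative: keep 25%, or change it. The stated method looks at one value only. Patients above a higher cut are a subset of those above 25%, so if OMRS change tracks symptoms at all, a split at 25% will tend to be associated with symptom change even when a different cut would separate patients better. A positive association then says that OMRS change carries information about symptoms, and nothing about where the threshold lies.

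The correlations in sections 6.2 and 3.5.4 do not fill the gap. They concern scores on whole scales and bear on validity; they compare no cuts.

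At stake is one of the two purposes that section 10.2 gives the pilot. As no accepted definition exists, nothing external would correct a poorly placed cut.

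**Working it through.** **The plan's own figures.** The documents give no figure for the assessment of the cut. The nearby figures in section 10.2 reproduce. With n = 34 and 75% response, the 95% half-width is 1.96 × √(0.75 × 0.25 / 34) = 14.6%, within the stated 15%. Exact enumeration of the one-tailed 0.10 Fisher test, 75% versus 35% with 17 per arm, gives 80.9% power against the stated 80%.

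**A case without simulation.** Take 34 patients. 26 have a fall of 25% or more (34 × 0.75 = 25.5). Suppose that 16 truly improved, all with falls of 40% or more.

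| | Improved | Not improved |
|---|---|---|
| Fall ≥ 25% | 16 | 10 |
| Fall < 25% | 0 | 8 |

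Two-sided Fisher p = [C(18,8) + C(16,8)] / C(34,8) = (43,758 + 12,870) / 18,156,204 = 0.003. The 25% cut is clearly associated with improvement, yet 10 of its 26 responders did not improve, and its specificity is 8/18 = 44%. A 40% cut would classify all 34 correctly. The p-value at 25% gives no hint of that.

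**Simulation.** From the documents: n = 34 and P(fall ≥ 25%) = 0.75. Assumed, because the documents are silent:
- percent fall is normal with SD 20 to 40 points (this ignores the ceiling at 100%), so its mean is 25 + 0.674 × SD, or 38.5 at SD 20;
- a yes/no patient anchor switches on at a true threshold of 25% or 40%;
- the anchor's underlying rating correlates 0.3 to 1.0 with percent fall;
- the association is tested by two-sided Fisher at 0.05.

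Percentage of trials in which the 25% split is significant:

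| Correlation | SD 20: truth 25% / 40% | SD 30: truth 25% / 40% |
|---|---|---|
| 1.0 | 100 / 95 | 100 / over 99 |
| 0.9 | 96 / 92 | 96 / 96 |
| 0.7 | 69 / 63 | 70 / 68 |
| 0.5 | 35 / 29 | 35 / 34 |
| 0.3 | 14 / 10 | 14 / 13 |

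At SD 40 no pair differs by more than 1.7 points. A second version, with the rating equal to percent fall plus noise, agrees within a point or two. Noise SD 10 on SD 20 gives correlation 20/√(400 + 100) = 0.89 and 97% versus 92%; correlation 0.5 gives 36% versus 31%. Across both versions the gap is never more than about 7 points.

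**Information lost by splitting.** The share kept by a split at proportion p is φ(z)² / [p(1 − p)]. At p = 0.75, z = 0.674 and φ(z) = 0.318, so the share is 0.101 / 0.1875 = 0.54. For a scale whose change correlates 0.5 with OMRS change, power at two-sided 0.05 is about 59% with the split and 87% with percent change as a continuous variable.

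**Can a search over cuts locate the threshold?** Only roughly. Choosing the cut from 10% to 65% with the largest Youden index gives, when 25% is true and the correlation is 0.5 or more, a median of 30 to 35 at SD 20 and 35 to 43 at SD 30. At correlation 0.5 and SD 20 the median is 35 (IQR 30 to 45) when 25% is true and 40 (IQR 32.5 to 45) when 40% is true. The search is pulled toward the centre of the distribution, and with weaker anchors the two cases can hardly be separated.

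**The case against.** The strongest reply is that section 10.2 is brief rather than wrong. It names no test and no rule that a positive association confirms 25%, it leaves modification open, and it presents the work on the instruments as secondary and preliminary. Sections 3.5.4 and 6.2 already correlate the scales, and OMRS scores are recorded at each visit (Appendix H), so other cuts can be examined later. This holds as far as it goes and limits the seriousness. It does not supply a method: the sentence ties the judgement to one level of change, and a comparison of cuts devised after the data are seen is weaker than one written down now.

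A reader might infer that the plan would endorse 25% even if the meaningful change were 40%. The documents do not support that as a general statement. It needs an anchor strongly related to OMRS change. At correlation 0.5 the split is significant in only about 3 trials in 10 when 40% is true, and at 0.3 in about 1 in 10. What holds at every strength examined is that the result is nearly the same when 25% is right.

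A reader might also infer that the best-separating cut should replace 25%. The Youden results above speak against it: when 25% is correct, the search tends to pick a higher value.

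A fair practical objection is that the only self-rating of change (Appendix D) asks about the past two weeks, while the primary OMRS change covers 28 days. No 28-day rating is collected, so the anchor has to be matched by interval.

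**Conclusion.** The point stands as a failure to discriminate. Association at the 25% cut is significant about equally often whether the meaningful change is 25% or 40%, with differences of at most about 7 percentage points over SD 20 to 40 and correlations 0.3 to 1.0. It also discards close to half of the information in percent change. The 40% value, the SD, the anchor strength, the Fisher test and the 0.05 level are assumptions. The nesting of cuts and the worked table do not depend on the SD or the anchor correlation.

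The effect is confined to what the pilot can say about a response definition for later trials. Nothing here shows that 25% is a wrong value, and the primary proportion, its interval and the comparison of arms are untouched. The change is worth making, but the trial's main result does not depend on it.

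**What to change.** Keep 25% as this trial's response definition and replace the sentence in section 10.2 with a short plan:

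- Relate percent change in OMRS, as a continuous variable, to change in the symptom scales, OHIP-14 and the Appendix B score.
- As an exploratory analysis, take the Appendix D global rating as the anchor. Report the OMRS percent change by rating category, and sensitivity and specificity at several candidate cuts (for example 10% to 60% in steps of 5), with bootstrap intervals that resample patients, since each contributes more than one interval.
- Match the OMRS change to the two-week recall, for example day 0 to 14 and day 14 to 28.
- Do not use the maximum-Youden cut as a decision rule. State that with 34 patients it is imprecise and pulled toward the centre of the change distribution, upward if 25% is the true value.

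The cost is a few lines of text and analysis on data already scheduled. The limitation is that two-week intervals inform the 28-day definition only indirectly; a direct answer would need a new 28-day rating item.

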## 2.4 RANDOMIZATION (OR STRATIFICATION) PROCEDURES:

[name] will create the randomization lists using variable block sizes. Patients will be randomized with a single stratification factor to try to ensure a balanced distribution among those getting placebo or not initially: being identified as having a high intensity of immunosuppression (2 or more agents/modalities  $\pm$  prednisone $\geq$ 0.5 mg/kg/day) vs. no or a lesser intensity of systemic immunosuppression according to the Intensity of Immunosuppression Scale.

Once patients have been evaluated and meet all eligibility requirements, patients will be registered with the NCI Central Registration Office and be randomized to either clobetasol or placebo. Change of systemic immunosuppressive regimen occurring after enrollment will not be allowed, and if this is necessary during the 2-week blinded phase of the study to control progressive systemic cGVHD, the patient will come off the study. Other medication changes will be documented at the interim or final (end of treatment) appointment and taken into consideration in the final analysis. However, given the small, pilot nature of the study, it is unlikely that the effect of all potential confounders can be meaningfully taken into account.

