## **3** STUDY IMPLEMENTATION

## 3.1 STUDY DESIGN

This is a randomized, double blind, placebo-controlled, pilot study of clobetasol 0.05% topical oral rinse with an open label cross-over or extension period. Consenting subjects with clinically significant oral chronic GVHD will be randomized to clobetasol 0.05% or placebo oral rinse. The placebo will be flavored with quinine, to approximate the "bitter" taste of clobetasol.

Subjects will be evaluated at bi-weekly intervals while on the study intervention. OMRS score will serve as the primary outcome measure. At the first 2 week interim appointment patients will be unblinded and started on the clobetasol oral rinse open label. In the absence of progressive oral disease on the scheduled interim evaluations during the 4-week clobetasol treatment period, all patients will complete a total of 4 weeks of treatment with clobetasol. Therefore, patients who were originally assigned to clobetasol arm will receive additional 2 weeks of treatment, and patients assigned to placebo arm will undergo an additional 4 weeks of treatment with clobetasol after unblinding. Patients with progressive disease after 2 weeks of therapy with clobetasol will be considered non-responders, taken off-treatment and treated as appropriate in consultation with primary clinician. Within 90 days of the end of the 1 month of treatment, all patients with evidence of benefit (response or stable disease) will be given an option to continue treatment with clobetasol 0.05% with or without additional treatment as deemed clinically necessary for 1 month after the conclusion of the initial treatment period. Additional follow-up appointment will be scheduled for all patients 1 month after completion of treatment. The change in OMRS scores from baseline to 4 weeks of mouth rinse usage will be the primary outcome variable. For the placebo group, the OMRS score at the end of the blinded phase/beginning of clobetasol rinse use (day 14) will serve as the baseline for the primary outcome. Difference in OMRS score between the groups (placebo and clobetasol) at the end of the 14-day blinded phase will serve as a secondary outcome measure. The study schedule of events is outlined in Appendix G.

# 

#	Because of problems with your teeth, denture or mouth have you	Never (0)	Hardly ever (1)	Occasionally (2)	Often (3)	Very Often (4)
1	Had trouble pronouncing words					
2	Felt sense of taste has worsened					
3	Had painful aching in the mouth					

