## 3.2.4 Treatment after 2 week blinded phase

Patients who switch to the clobetasol arm due to initial placebo assignment will be treated with clobetasol 0.05% oral rinse for 4 weeks. Patients originally assigned to clobetasol arm will be treated for another 2 weeks.

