## 3.6.1 Compliance

Subject adherence to the trial interventions will be estimated by measuring the volume of the remaining study medication at follow up appointments, study medication use diaries (Appendix I) and compliance with clinic visits. Correct use of the study medication will be demonstrated at the beginning of the study. Reinforcement such as periodic phone calls by the study nurses will be used to maximize compliance.

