## 3.8.2 Off-Study Criteria

- Progressive oral cGVHD after 2 weeks of treatment with clobetasol: Patients will be unblinded at the time of GVHD progression and taken off study as defined in Section 6.3.1.
- Unacceptable toxicity: we do not expect significant adverse events associated with the study medication or procedures. In the event of unexpected toxicity attributable to the study drug (grade 2 or greater) patients will be taken off study.
- Patients unable to comply with study requirements will come off study. This includes  $\geq$ 75% non-compliance with study oral rinse usage.
- Patients will come off study upon completion of follow-up Period (6 months after discontinuing clobetasol oral rinse treatment).
- Death
- Patient lost to follow up
- Patient withdrawal from follow-up period
- Change in the systemic immunosuppressive therapy while in the 2 week blinded phase
- PI decision to end this study

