The primary endpoint is the fraction of subjects who experience a 25% improvement in their OMRS compared to their own baseline. The fraction will be estimated with a two-tailed 95% confidence interval as the primary outcome. This will be done using all 34 patients together provided that the changes from baseline to day 28 for the two groups are sufficiently similar. A formal test will be performed assess their comparability. This will be determined conservatively, by obtaining the actual difference in the individual OMRS for each patient at baseline (day 0 for initial clobetasol and day 14 for those initially given placebo) vs. the value after day 28 of clobetasol and comparing those differences between the two randomized groups using a two-tailed Wilcoxon rank sum test. If the p-value for that comparison is >0.30, then the two groups will be considered sufficiently similar to allow pooling of the results and to report a combined

fraction of patients who have a 'response' to 28 days of clobetasol. In this case 34 patients will be sufficient to allow the proportion of patients with a response of 75% or more to have a two-sided 95% confidence interval of +/- 15% or less, which will be considered sufficiently precise. Fractions of responses <75% would have slightly wider confidence interval widths.

An important secondary endpoint is to compare the changes from day 0 in the OMRS until day 14 between those who only receive placebo by that point vs. those who received clobetasol. This evaluation will be done both with respect to the fraction with a response by 2 weeks, as well as comparing the actual changes in OMRS from day 0 to day 14.

By enrolling 17 patients per arm, a 0.10 alpha level one-tailed Fisher's exact test will have 80% power to detect a difference between a potential 75% of patients having a 25% or greater decrease in severity score on the clobetasol arm and about half that amount, 35%, on the placebo arm. A one-tailed test is sufficient for this secondary objective in this study since we will not expect clobetasol to be associated with a lower fraction of patients with benefit compared to placebo and because this is intended to be a pilot study to determine if a potential trend of magnitudes anticipated, but not necessarily a statistically significant gain, may be detected. Should very promising results be obtained, then a subsequent trial could be conducted to build upon and further confirm the benefit noted.

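### Section 10.2 deletes patients with 75% or more non-use after randomisation, and no all-randomised analysis is planned, even for the day-14 placebo comparison

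*Combined protocol and SAP*

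**What the plan says.** Section 3.8.2 makes a patient's failure to comply an off-study criterion, at or above "75% non-compliance with study oral rinse usage". Section 10.2 then removes these patients from the results: those at or above "75% non-use of the oral rinse, will not be included in the data analysis". As extracted, that sentence has no closing full stop, so a lost qualifier cannot be ruled out. As it stands, it exempts no endpoint.

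Other departures are treated differently. Patients off study for oral progression count as non-responders. So do the rest: "Patients taken off study for reasons unrelated to the primary outcome will be classified as non-responders and analyzed accordingly".

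Section 3.6.1 says that adherence is "estimated by measuring the volume of the remaining study medication at follow up appointments", together with diaries and visit attendance. It does not say over which period the 75% is counted. The period matters because treatment has two parts. Under Section 3.1, "At the first 2 week interim appointment patients will be unblinded and started on the clobetasol oral rinse open label". Under Section 3.2.4, "Patients originally assigned to clobetasol arm will be treated for another 2 weeks", while the placebo arm receives four weeks of clobetasol.

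Section 10.2 also plans, as an important secondary endpoint, to "compare the changes from day 0 in the OMRS until day 14 between those who only receive placebo by that point" and those who received clobetasol. The size target is 34 evaluable patients (17 per arm) with a ceiling of 40 enrolled. *Evaluable* is not defined, and no all-randomised analysis is planned for any endpoint.

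**The concern.** Non-use is observed after randomisation and may be related to lack of benefit or to tolerability. Deleting non-users can therefore leave two arms that no longer differ only by chance and treatment. Three consequences follow.

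- **Day-14 comparison.** It is secondary, but it is the only controlled evidence in the trial. If non-users are unbalanced between arms and tend not to respond, the test is distorted.
- **28-day fraction.** The primary outcome is a single proportion on clobetasol. It rises whenever non-responding non-users are removed.
- **Undefined period.** On a per-phase or clobetasol-only count, open-label non-use after unblinding could delete a valid blinded day-14 score.

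The two handling sentences in Section 10.2 can also overlap: a non-user whose reason has nothing to do with the outcome falls under both, with opposite results.

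A smaller problem runs the other way. Under Section 2.4, where a change of systemic immunosuppression is needed, "if this is necessary during the 2-week blinded phase of the study to control progressive systemic cGVHD, the patient will come off the study". Read literally, the sentence on unrelated reasons counts a placebo patient who leaves this way as a non-responder to 28 days of clobetasol, although that patient never received it.

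**Working it through.** **Inputs (Section 10.2).** 17 per arm; assumed response 75% on clobetasol and 35% on placebo; one-sided Fisher's exact test at 0.10; stated power 80%; 34 evaluable of at most 40 enrolled. No non-use rate is given, so every count of non-users below is an assumption.

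**1. The plan's own figure.** Let X ~ Bin(17, 0.75) and Y ~ Bin(17, 0.35), and sum P(X=x)·P(Y=y) over all tables with one-sided Fisher p ≤ 0.10. Power = 0.809. The stated 80% reproduces, so the arithmetic is sound and the issue is the analysis population.

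**2. Can open-label non-use remove a blinded day-14 score?** Take a patient fully compliant while blinded who uses nothing afterwards.
- Clobetasol arm: 14 of 28 days missed = 50%.
- Placebo arm: 28 of 42 days missed = 67%.

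On a cumulative count neither reaches 75%. To reach it, the patient must also miss (0.75×28 − 14)/14 = 50% of blinded doses in the clobetasol arm, or (0.75×42 − 28)/14 = 25% in the placebo arm. Counted per phase or on clobetasol alone, open-label non-use is 100% and the patient is excluded.

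**3. False-positive rate of the day-14 test.** Both arms respond at 35%. Randomise 17+k to clobetasol and 17 to placebo, remove k non-responders from clobetasol, and sum the probability of p ≤ 0.10. With no exclusion at 17 v 17 the rate is 5.3%.

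| k (clobetasol arm only) | k excluded | same patients kept |
|---|---|---|
| 1 | 7.1% | 4.9% |
| 2 | 9.3% | 5.2% |
| 3 | 11.8% | 5.3% |

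Excluding 3 non-responders from each arm of 20 gives 6.8%. Excluding 3 from placebo only gives 2.7%. Starting instead from 20 per arm and excluding 1, 2 or 3 from clobetasol only gives 6.8%, 8.4% or 12.3%, so the 0.10 level is again crossed at three.

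**4. Effect on p at counts nearest the plan.** One-sided Fisher:
- 13/17 v 6/17: p = 0.018
- three clobetasol non-users restored as failures, 13/20 v 6/17: p = 0.070
- three restored in each arm, 13/20 v 6/20: p = 0.028

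All stay below 0.10.

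**5. 28-day fraction.** 26/34 = 76.5%. With one excluded non-user counted as a failure, 26/35 = 74.3%. With six, which uses the whole 34-to-40 allowance, 26/40 = 65.0%. In the opposite direction, counting 1 to 4 never-treated placebo patients among the 34 lowers a true 75% to between 0.75×33/34 = 72.8% and 0.75×30/34 = 66.2%.

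**The case against.** The strongest reply is that material harm needs a worst case. The 0.10 level is exceeded only with no drug effect and three non-users, all in the clobetasol arm and all non-responders. If non-use is unrelated to outcome, the rate stays at 5.3%.

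The design also works against imbalance. The placebo is quinine-flavoured and meant to match in appearance and taste, the blinded phase lasts 14 days, and diaries, volume checks and phone calls support adherence. The 75% threshold is extreme, and most other leavers are already kept. Section 10.2 calls the trial a pilot looking for a trend and acknowledges its limitations. Loss of a day-14 score through open-label non-use requires a counting rule that the text does not state. Never-treated placebo patients might be meant to fall among the inevaluable.

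Much of this stands as a limit on size: the bias is probably small if exclusions are few or balanced. It does not remove the point. The exclusion is a stated rule, no analysis shows its effect, and the text does not settle the counting period or who is evaluable.

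A fair further point concerns cost. If 1, 2 or 3 non-responding non-users are added to the clobetasol arm only, as-randomised power is 70%, 69% or 57%, against 81% when they are excluded. That belongs in the account. It describes what an as-randomised comparison can detect when non-users fall in one arm; it is not a defect of the proposed analysis.

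**Conclusion.** The concern holds and should be fixed. Section 10.2 removes patients on the basis of post-randomisation behaviour, across all endpoints as written, with no all-randomised analysis beside it.

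For the day-14 test, one or two one-sided exclusions in the clobetasol arm keep the false-positive rate below 0.10, and three take it to 11.8%. Balanced exclusion has little effect, and at counts near the plan the conclusion does not change. For the 28-day fraction, the shift runs from about 2 points with one excluded non-user to 11.5 points with six (76.5% to 65.0%). The literal handling of never-treated placebo patients pushes the fraction down, so the net direction is unknown.

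These sizes assume the counts shown and that excluded patients do not respond. Deletion of blinded scores through later non-use is possible only if non-use is not counted cumulatively.

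**What to change.** In Section 10.2 and the accrual text:

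- **Day-14 response:** analyse all randomised patients in their assigned arm, using the observed day-14 OMRS whatever the compliance, and non-response if it is missing.
- **28-day fraction:** analyse all patients who start clobetasol, with a missing day-28 score as non-response. Report separately, with reasons, the placebo patients who leave before clobetasol.
- **Sensitivity analysis:** keep the exclusion of patients with 75% or more non-use here, and state the period over which non-use is counted.
- **Definitions:** define *evaluable* to match, and state that the Wilcoxon and paired tests use observed scores.

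The missing-data rule is needed because Section 3.3.3 asks for the off-treatment assessment only where it can be obtained. Appendix G schedules the first compliance check and the OMRS at the same day-14 visit, so many non-users should have a usable score.

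**Cost.** Wording only, with no new data collection, and possibly a lower reported fraction. Day-14 power is 81% at 17 per arm. With 1, 2 or 3 non-responding non-users per arm, it is 77%, 73% or 68% if they fall within the 17, and 81%, 81% or 71% if they are enrolled in addition. If they are added to the clobetasol arm alone, it is 70%, 69% or 57%. All of these counts are assumed.
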